### 4. Host immune responses:

Functional properties of cytotoxic T cells and NK cells will be correlated to changes in total HIV-1 DNA and IUPM. Flow cytometry data will be evaluated by Boolean partitioning of NK and T cell responses into distinct responding populations (Lamoreaux et al., 2006).

Finally, linear regression will be used to identify predictors of log-transformed time to viral rebound in both arms. P values  $<0.05$  will be considered statistically significant.

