
Statistical Methodology
	
The Wilcoxon-Mann-Whitney will be used to determine changes from baseline to the pre-ATI time-point in reservoir size for each group. Fishers exact or chi-square test will be used to compare the proportion of subjects in both groups with detectable viremia during each romidepsin treatment. Functional properties of cytotoxic T cells and NK cells will be correlated to changes in total HIV-1 DNA and IUPM. Flow cytometry data will be evaluated by Boolean partitioning of NK and T cell responses into distinct responding populations (Lamoreaux et al., 2006).
 
Finally, correlation analysis will be performed to identify the markers most likely associated with time to viral rebound. As exploratory analysis, a linear regression model will be used to determine predictors of log-transformed time to viral rebound in both arms. P values <math><0.05</math> will be considered statistically significant.

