#### **6.1.7 ART interruption and re-initiation of combination ART**

ART regimen will be discontinued at week 24, 16 weeks after the second 3BNC117 infusion. ART will be discontinued for 12 weeks and if viral rebound does not occur, subjects can remain off ART with continued follow up.

At week 36, if a subject's HIV-1 VL remains undetectable, the subject will have the option to restart ART at that time or to continue weekly follow up through the end of the study (week 48). During the ATI, ART will be resumed if plasma HIV-1 RNA level  $\geq$  200 copies/ml in 2 consecutive measurements or if CD4+ count drops  $<$  350 cells/ $\mu$ l and the result is confirmed upon repeat measurement. In this case repeat measurements are performed at the next scheduled visit. If the HIV-1 RNA level is found to be  $\geq$  1000 copies/ml the subject will be contacted to return to clinic as soon as the result becomes available. Upon viral rebound, viral genotyping will be performed to determine if any resistance mutations are present. ART will also be reinitiated if the participant becomes pregnant, or if otherwise clinically indicated.

Subjects who experience viral rebound during the ATI will be followed on a modified schedule (Appendix B). These subjects will have study visits every 2 weeks until their HIV-1 VL is undetectable on 2 consecutive measurements. At that point, they will be followed every 8 weeks until the final visit at week 48.

Subjects' primary care physicians will be contacted when virologic rebound occurs and periodically throughout the study.

During ATI phase of the study subjects may be at increased risk of transmitting HIV to their partners and of HIV-1 superinfection from an HIV-infected partner. Therefore, subjects will be asked to use male or female condoms for the duration of ART interruption. In the event of a high-risk exposure to an HIV-infected partner, a subject may re-initiate ART as clinically indicated by his/her HIV primary care physician.

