### **8 Data Analysis**

#### **8.1 Analysis of Antiretroviral effects, Safety and Pharmacokinetics**

##### **Primary Endpoint:**

1. Days to viral rebound during ATI or days to reinitiation of ART in participants who restart ART before viral rebound. Viral rebound is defined as HIV-1 RNA  $\geq$  200 copies/ml on 2 consecutive measurements during ATI. If viral rebound occurs, the

date of the first measurement of HIV-1 RNA  $\geq 200$  copies/mL will be defined as “date of viral rebound.” As primary analysis, we will use the Wilcoxon-Mann-Whitney test to compare the median time to viral rebound between the two study groups. As secondary analysis, we will use the Kaplan-Meier estimator and log-rank test to assess the significance of the difference between the survival curves in the two study arms.

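### The exploratory regression of log time to rebound has no rule for participants who do not rebound; the bias is negligible on the plan's own inputs but material if about 10% or more do not rebound

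*Combined protocol and SAP*

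**What the plan says.** Section 8.1, under host immune responses, plans that "linear regression will be used to identify predictors of log-transformed time to viral rebound in both arms", judged at P<0.05. The synopsis has the same model and gives its status: "As exploratory analysis, a linear regression model will be used to determine predictors of log-transformed time to viral rebound in both arms". Neither place names a method for censored data.

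The outcome is defined in sections 3.4 and 8.1 as days to rebound, or "days to reinitiation of ART in participants who restart ART before viral rebound". Section 6.1.7 sets the length of the interruption: "ART will be discontinued for 12 weeks and if viral rebound does not occur, subjects can remain off ART with continued follow up". A participant still undetectable at week 36 may restart ART then or be followed weekly to week 48. No section gives an outcome value to someone who reaches week 48 suppressed and off ART.

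For the comparison of arms, section 8.1 does use methods that handle censoring: "As secondary analysis, we will use the Kaplan-Meier estimator and log-rank test". They are not extended to the marker regression.

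**The concern.** The hypothesis in section 3.2 covers prevention of rebound as well as delay, so the design allows for participants whose rebound time is known only to exceed their time under observation. Linear regression needs a number for each person. The analyst must either enter the stopping date as if it were a rebound date or leave the person out, and the plan does not say which.

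The choice can matter. Two participants with equal control could be entered at 84 days (restart at week 36) or 168 days (week 48) because one preferred to restart. On the log scale that gap is ln 2 = 0.69, more than the whole log-scale SD of about 0.53 implied by the plan's inputs (step 2 of the working).

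Section 3.1.1 lists correlates of time to rebound among four knowledge gaps that the study will address. Participants with the longest control carry much of that information, and they are the ones this model cannot place.

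**Working it through.** **1. The plan's own figure.** The documents give no figure for the regression. They do give the inputs of the power calculation in section 8.2: SD 10 days, difference 13 days, 12 per arm, 5% level, minimum asymptotic relative efficiency (0.864).
- Effective n per arm = 12 × 0.864 = 10.37.
- Noncentrality = (13/10) × √(10.37/2) = 2.96, with 2 × 10.37 − 2 = 18.7 degrees of freedom.
- Two-sided power is 80.1%, against the stated 80%. The inputs reproduce and can be used below.

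**2. How many would be censored on those inputs?** Section 3.1.1 puts rebound at 2–3 weeks in most people. Take a mean of 17.5 days in arm B, 17.5 + 13 = 30.5 days in arm A, SD 10 days, and a log-normal shape (assumption).
- Arm B: log-variance = ln(1 + (10/17.5)²) = 0.283, log-SD 0.53, log-mean = ln 17.5 − 0.141 = 2.72. P(no rebound by day 84) = 1 − Φ((4.43 − 2.72)/0.53), about 0.06%.
- Arm A: log-SD 0.32, and the same probability is about 0.04%.
- Over arm B means of 14 to 21 days, the range is 0.04% to 0.09% per arm by day 84, and at most 0.0014% by day 168.

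**3. Effect on a marker slope.** I simulated 30 participants (15 per arm), with log time = constant + arm effect + slope × marker + normal error. The log-SD within arm is 0.53 and the marker correlation 0.5 (assumption), with 800 runs per row. The arm effect is ln(30.5/17.5) in the plan-input and early-restart rows and zero in the 10–30% rows. Entries are mean fitted slope divided by true slope.

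| Scenario | Stop counted as rebound | Non-rebounders dropped | Censored log-normal model |
|---|---|---|---|
| Plan inputs, stop at day 84 (0.9% censored) | 1.00 | 0.97 | 1.01 |
| Plan inputs, stop at day 168 (0.0%) | 1.00 | 1.00 | 1.00 |
| Assumed 10% non-rebound at a common stop | 0.90 | 0.77 | 1.01 |
| Assumed 20% | 0.81 | 0.65 | 1.02 |
| Assumed 30% | 0.68 | 0.55 | 0.99 |
| 10% early restart, unrelated to marker | 0.99 | 0.99 | 1.00 |
| Early restart more likely at low marker values (17% censored) | 1.35 | 0.98 | 0.82 |

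Monte Carlo error is 1–2% per entry. The first row has more censoring than step 2 because it keeps the log-SD at 0.53 in arm A too, which widens that arm. In the 10–30% rows the common stop is placed at the matching quantile; in this model the ratios depend on the fraction censored and the marker correlation, not on the calendar day.

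**4. A second setting.** With 24 participants, slope 0.6, residual SD 0.6 (assumptions) and 16% without rebound at day 84, the ratios are 0.85 (stop as rebound) and 0.78 (dropped); the censored model is within about 2% of 1. The spread this needs is large. The log-SD is √(0.6² + 0.6²) = 0.85 and the median is exp(ln 84 − 0.85 × 0.99), about 36 days. The mean is then 36 × exp(0.36), about 52 days, and the SD is 52 × √(exp(0.72) − 1), about 53 days. The plan assumes 10.

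**5. The last row of the table.** There each early restart falls at a random fraction of that participant's own rebound time, so the censoring is informative. Counting the restart as rebound then inflates the slope, and the censored model understates it.

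**The case against.** A reader might infer that marker effects in this trial will be biased toward zero. The documents do not support that, for three reasons.
- They give no non-rebound rate, and their own inputs imply that almost nobody is censored by day 84.
- Day 84 is the earliest optional stop; follow-up off ART can run to day 168, which lowers the censored fraction further.
- The direction is not fixed. With marker-related early restart the slope ratio was 1.35, and the censored model (0.82) did worse than dropping those participants (0.98).

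A reader might also infer that using the restart day is a coding error. It is not: the composite endpoint assigns that day to people who restart before rebound. What can be disputed is whether a composite suits a question about markers of rebound. Only participants suppressed and off ART at week 48 lack a value.

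The analysis is exploratory, and the synopsis separately plans a correlation analysis of markers with time to rebound, so the knowledge gap does not rest on this model alone. The phrase about both arms may also mean separate fits of 12–15 people, which the simulation does not represent.

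All of this limits the size and certainty of the point. It does not supply the missing rule. The power inputs describe a 13-day delay, not the preventive half of the hypothesis, and that is where censoring would arise.

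**Conclusion.** The gap is real and the bias conditional. The planned regression does not account for censoring that the design permits, and one group of participants has no defined outcome.

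Under the plan's own inputs the runs show a bias of 0–3%; allowing for Monte Carlo error, call it nil to about 5%. If about 10% or more do not rebound by a common stopping date, slopes shrink by roughly 10–30% with the stop counted as rebound, and by a similar or larger amount if those participants are dropped. These figures rest on an assumed non-rebound rate, a log-normal shape and an assumed marker correlation. If early restart is related to the marker, the bias can reverse.

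The primary Wilcoxon-Mann-Whitney test, the log-rank comparison and the sample size are unaffected. The change is worth making because it is cheap and loses little if everyone rebounds.

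**What to change.** In section 8.1 and the synopsis:
- Replace linear regression with a log-normal accelerated failure-time model (or a Cox model) that includes an arm term. Say whether the arms are pooled or fitted separately.
- Censor participants who restart ART without rebound on the restart date, and those still without rebound at the end of follow-up on their last measurement date.
- State that this assumes non-informative censoring, given the covariates in the model.
- Add a sensitivity analysis that counts ART restart as an event, as the composite endpoint does, and report the number and timing of restarts without rebound.

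With no one censored, the log-normal model gives the same coefficients as linear regression on the same covariates. Its standard errors use a divisor of n instead of n minus the number of coefficients, so P values in a sample this small will differ slightly; the plan should name the test to be used. The cost is a change of wording, with no new data or visits.

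The amendment should be made before rebound data are examined.

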#### 5. Other measurements:

The frequency and levels of anti-3BNC117 antibodies, after each 3BNC117 infusion, will be calculated and displayed in tables. Levels of romidepsin will similarly be calculated and displayed in tables. Pharmacokinetic parameters will be calculated using standard non-compartmental analysis methods, using WinNolin software, version 6.4. Pharmacokinetic parameters, including AUC, Cmax, T1/2, Tmax and others will be summarized.

Genotyping of HIV-1 isolates will be performed by reverse transcription followed by PCR amplification and sequencing of HIV-1 envelope genes. Sequence analysis to identify potential 3BNC117-induced escape mutations will be descriptive.

Continuous data will be summarized by descriptive statistics, including the sample size, mean, standard deviation, median and range. Categorical data will be summarized by the number and percentage of participants. If necessary Log2 of variables will be used.

### **8.2 Sample Size Considerations**

The sample size calculation is based on the primary analysis for the primary endpoint. We will compare days from day of ART interruption until day of viral rebound or day of reinitiation of ART without viral rebound in arm A to arm B (1:1 randomization) with the Wilcoxon-Mann-Whitney test. Given a standard deviation (SD) of 10 (days), enrolling 12 patients in each of the two arms, will have 80% power to detect  $\geq 13$  days difference in time to viral rebound at a 5% significance level ([Davey et al., 1999](#); [Hamlyn et al., 2012](#); [Hill et al., 2014](#)). The power calculation for this primary analysis was performed in G\*power using the minimum Asymptotic Relative Efficiency method.

To accommodate for dropouts, we aim to enroll 30 study subjects in the study (15 in each arm). A dropout rate of ~20% is anticipated.

### **9 Data and Sample Storage**

The Principal Investigator(s) will oversee how the data are collected, entered, and protected. All study data will be collected by the clinical study staff using designated source documents and entered onto the appropriate electronic case report forms (eCRFs). Clinical Trials Centre Cologne will provide a secure web-based database that will be used for data management. Data collection forms (DCFs) will be provided for use as source documents as appropriate. All study data must be verifiable to the source documentation.

All source documents will be kept in a locked facility at the clinical sites and remain separate from volunteer identification information (name, address, etc.) to ensure confidentiality. All data with volunteer identifiers will be kept in a locked facility and/or encrypted files. Source documentation will be available for review to ensure that the collected data are consistent with the eCRFs.

All eCRFs and laboratory reports will be reviewed by the site's clinical team, who will ensure that they are accurate and complete.

All research samples will have a unique identifier. The site PI will be responsible for ensuring project compliance, data analysis and entry, regulatory monitoring, and coordination of the activities of the entire study team. Standard GCP practices will be followed to ensure accurate, reliable and consistent data collection.

Source documents include, but are not limited to:

- Signed Informed Consent Documents
- Dates of visits including date of 3BNC117 and romidepsin infusions
- Documentation of any existing conditions or past conditions relevant to eligibility
- Reported laboratory results
- All adverse events
- Concomitant medications

## **10 Recruitment Plan**

Both men and women ages 18 through 65 will be recruited for the study from the community at large and will be referred by physicians in the community. We will make every effort to recruit minorities and women. We project screening 60 subjects in order to achieve at least 30 evaluable subjects. Enrollment will be competitive across the three trial sites. In case of drop-outs an over-enrollment of 10% will be allowed.

- At RUH, the Clinical Research Support Office at the Rockefeller University Hospital (CRSO) will utilize the Volunteer Repository. Advertisements will also be placed: online (e.g. Craigslist, CenterWatch, etc.), in newspapers (Metro, AMNY) and on campus. In addition, participants will be recruited at Montefiore Medical Center. Recruitment fliers will be placed in the clinic, and interested participants will contact study recruiters at Montefiore. The pre-screening procedure will take place over the phone or in person at Montefiore clinic. Recruiters will collect participant's medical history and other relevant information and will provide the participant a brief description of the study. Potential participants will also have an opportunity to ask questions about the study. If participants show interest and agree to be contacted, their contact information will be shared with Rockefeller site investigators (via secure email) for scheduling of screening visit. Informed consent and all other study-related procedures will occur at the Rockefeller site.
- At AUH, written invitations to participate in the study will be sent to eligible HIV patients.
- At UCH, eligible HIV infected individuals will be invited by phone to participate in the study.

## **11 Potential Benefits to Subjects**

It is unlikely that study subjects will benefit from participating in this study.

## 12 Potential risks to the subject

- This study entails moderate risk to subjects since 3BNC117 is an investigational new drug with limited human safety data and romidepsin has potential side effects. The study also includes a period of ART interruption. It has been shown that episodic ART guided by CD4+ count decline leads to increased risk of opportunistic infections as compared with continuous ART (Strategies for Management of Antiretroviral Therapy Study et al., 2006). However, different groups have now shown that short analytical treatment interruption is safe (Routy et al., 2012). ART will be resumed if plasma HIV-1 RNA levels increase to  $\geq 200$  copies/ml and are confirmed upon repeated measurement.
- If the HIV-1 viremia rebounds after ART is discontinued, absolute CD4+ counts might drop. However subjects will be followed very closely and ART will be resumed if the CD4+ cell count drops  $< 350$  cells/ $\mu$ l and this is confirmed upon repeat measurement.
- During ART interruption, subjects might experience symptoms of acute retroviral syndrome, such as fever, rash, lymphadenopathy, headache, sore throat, nausea, vomiting. ART will be resumed if acute retroviral syndrome is suspected by study investigators.
- Resistant viral strains to previous ART medications might arise during the analytical treatment interruption.
- During the ART-interruption phase of the study subjects may be at increased risk of transmitting HIV to their partners, if they become viremic, and of HIV-1 superinfection from an HIV-infected partner. Therefore, subjects will be asked to use male or female condoms for the duration of ART interruption. In the event of a high-risk exposure to an HIV-infected partner, a subject may re-initiate ART as clinically indicated by his/her primary care physician.
- 3BNC117 has now been administered to 63 volunteers and was generally safe and well tolerated in all doses tested. To date, 8 ART-treated HIV-infected individuals have received two 3BNC117 infusions, administered 3 weeks apart. This is the first time 3BNC117 will be administered in combination with romidepsin.
- While each mAb product has unique safety issues related to its mechanism of action, the major safety concern related to mAbs in general is an infusion/hypersensitivity reaction. These types of reactions are more common for mAbs that contain murine elements compared to human mAbs, such as 3BNC117. Passive administration of anti-HIV-1 antibodies has been evaluated in humans in the past. As observed with other monoclonal antibodies, anti-HIV-1 antibodies were generally safe and well tolerated and most adverse events observed were infusion-related events. (Mehandru et al., 2007b; Trkola et al., 2005b).

- Immunologic symptoms such as listed below are possible with administration of a monoclonal antibody and will be considered adverse events of interest. Potential allergic-type reactions during and immediately following the administration of 3BNC117 will be carefully monitored.
  - Constitutional symptoms, such as fever, rigors/chills;
  - Injection site reaction/extravasation changes, pruritus, urticaria;
  - Serum sickness like syndromes as evidenced by fever, rash, arthralgia, arthritis, nephritis;
  - Deposition of immune complexes in the kidneys leading to renal insufficiency;
  - Adult Respiratory Distress Syndrome, bronchospasm/wheezing, anaphylaxis;
  - Cytokine release syndrome/ acute infusion reaction.
- 3BNC117-resistant viral strains might arise following administration of 3BNC117. Development of 3BNC117 resistance might limit the future use of 3BNC117 by the study subject, if this monoclonal antibody is licensed for clinical use by the FDA.
- In the cross-reactivity study in human tissues, 3BNC117 was found to bind to cells in the conjunctival recesses. It is possible that this binding could lead to conjunctival toxicity. However, when rats and non-human primates were administered 3BNC117, conjunctival toxicity was not observed. Sixty-three participants have received 3BNC117 to date, and 12 participants reported mild ophthalmic complaints (such as pruritus, conjunctival erythema, increased lacrimation) during study follow up. In all instances symptoms resolved without specific treatment and ophthalmologic evaluations 5 months after 3BNC117 administration did not show changes from baseline.
- The adverse effects 3BNC117 administration would have in a fetus or unborn child are unknown.
- Most studies with romidepsin were performed in patients with severe haematological malignancies and used doses up to 15 mg/m^2. The most common adverse events associated with romidepsin involve the GI system (nausea, vomiting, diarrhea/constipation), hematologic condition (thrombocytopenia, leucopenia (neutro- and lymphopenia) and anemia), asthenic conditions (asthenia, fatigue, malaise and lethargy) and finally electrolyte abnormalities (hypomagnesiemia, hypokalemia and hypocalcemia), hyperglycaemia and pyrexia. Overall, the most common grade 3/4 events reported were anaemia, thrombocytopenia, neutropenia, leukopenia and fatigue.
- QT prolongation as well as several morphological changes in ECGs (including T-wave and ST segment changes) has been reported in clinical studies of romidepsin. Many of the ECG morphologic abnormalities were also observed at baseline. These ECG changes were transient and were not associated with functional cardiovascular changes or with symptoms. The clinical significance of these changes is unknown.

- In a pilot study in 6 HIV-1-infected participants on long-term ART, who received 3 infusions of 5 mg/m^2 of romidepsin over the course of 3 weeks, no serious adverse events (SAEs) or suspected unexpected serious adverse reactions (SUSAR) was observed. Thirty-five AEs were considered related to romidepsin. All drug-related AEs were mild (grade 1, n=35) and resolved spontaneously within a few days. The most common romidepsin-related AEs were abdominal symptoms (e.g. nausea [n=11], borborygmia [n=4], abdominal pain [n=2]) and fatigue (n=5). Modest changes in white blood cell counts (WBC) and T cell counts were observed during the study. Neutrophil counts below 1000 cells/mm^3, CD4+ cell counts below 350 cells/mm^3, or platelet counts below 100,000 cells/mm^3 were not observed.
- A theoretical risk of HDAC inhibitors is that they will induce activation of other retroviruses, oncogenes and/or DNA viruses, including CMV, hepatitis B virus and JC viruses. However in a study in HIV-infected participants who received panobinostat over a course of 8 weeks (another HDAC inhibitor), CMV DNA (in urine) and EBV DNA (in blood) were monitored and there was no evidence of unintended virus reactivation.
- Clinical data is not available with romidepsin during pregnancy. In this study, use of two contraceptive methods for both female and male study subjects is required for the duration of the study.
- Based on non-clinical findings in repeat-dose toxicity studies, romidepsin has the potential to affect male and female fertility. Testicular atrophy or degeneration occurred in rats at doses corresponding to 1.98 mg/m^2. In dogs, romidepsin caused hypospermia at doses corresponding to  $\geq 20$ mg/m^2. In rats, at doses  $\geq 0.1$  mg/kg/week corresponding to 0.6 mg/m^2 or a mean steady state AUC0-∞ 4.9 ng·hr/mL, females exhibited atrophy in the ovary, uterus, vagina and mammary glands. Further, maturation arrest of ovarian follicles was observed in female rats at  $\geq 0.3$  mg/kg/week corresponding to 1.8 mg/m^2. It is not known if romidepsin can impair fertility in humans, although since the FDA approval of romidepsin in 2009, no cases of fertility-related adverse effects have been reported. If romidepsin does result in ovarian or testicular atrophy, symptoms related to decreased sex hormone production could also occur, such as early menopause, decreases in bone density or libido, and alterations in mood or body habitus. Until now, however, such symptoms have not been observed among HIV patients (n=23) receiving romidepsin at a dosing of 5 mg/m^2 in other experimental trials (Søgaard et al. 2015, Leth et al. 2016).
- Blood drawing and phlebotomy can be associated with pain, bruising, anemia or infection at the site of venipuncture. Rarely, fainting may follow phlebotomy.

